The primary outcome will be total β -OHB as represented by the area under the curve across 4 hours. Secondary outcomes include blood glucose, blood pressure, heart rate, taste and supplement acceptability, hunger and fullness, and gastrointestinal tolerability - all measured across the 240-minute post-supplementation period. Blood samples will be collected via finger prick; blood β -OHB and glucose levels will be measured using the "Keto-Mojo" handheld monitor at baseline and 15, 30, 60, 90, 120, 180, and 240 minutes after ingestion of the ketone supplement.

Visits Summary

The study will involve a total of 3 visits to the laboratory.

Visit 1: Baseline screening & first experimental trial (duration 270 minutes)

Individuals will be recruited by word-of-mouth. Individuals must be able to read and understand English in order to understand the study instructions. On the initial visit, the potential participant will read through the information and consent form, be able to ask any questions, and provide written informed consent. The research lead ([name] Candidate) will ensure that the participant understands the details of the study and consent form.

Inclusion criteria will be: i) over the age of 18; and ii) able to fast overnight. **Exclusion criteria** will include: i) being a competitive endurance athlete; ii) following a ketogenic diet, low-calorie diet, periodic fasting regimen, or regularly consuming ketogenic supplements; iii) being unable to travel to and from the university; iv) being unable to follow the diet instructions; v) being pregnant or planning to become pregnant during the study; vi) having been diagnosed with a chronic disorder of glucose or fat metabolism, including type 2 diabetes, chronic pancreatitis, or gallbladder disease; vii) being unable to read or communicate in English.

Females will complete the menstrual cycle questionnaire to confirm they are in the follicular phase. Anthropometric and physiologic measurements will be collected (height, body weight, waist circumferences, blood pressure) for baseline participant characterization. The research lead will review the dietary record with the participant and confirm the participant is fasted and has refrained from structured exercise and alcohol the day prior.

A baseline finger prick will then be performed before ingestion of the ketone supplement. Another 7 finger pricks will be performed at 15, 30, 60, 90, 120, 180,

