and 240 minutes after ingestion of the supplement. Throughout the 240-minute period, participants will be allowed to do quiet work or perform other sedentary activities (reading, watching a movie). Participants will be asked to complete the questionnaire on gastrointestinal discomfort 60 minutes after ingestion of the supplement, and the questionnaires on hunger and fullness as well as taste and supplement acceptability at the end of the 240-minute post-supplementation period.

At the end of the visit, the participant will be reminded to consume the same diet on the day before the next experimental trial, and to refrain from structured exercise and alcohol consumption in the 24 hours prior.

Visits 2 & 3: Second and third experimental trial (duration 240 minutes)

The second and third experimental trial will be identical to the first visit (except no baseline anthropometric measurements will be performed), with the only difference being the different ketone supplement provided to the participant.

Statistical Analyses

Descriptive statistics (means, SD, and frequencies) will be calculated. Significance will be set at P < 0.05. Data across time will be analyzed in R using a linear mixed effects model with subjects as a random factor and condition and time as fixed factors. Assumptions will be tested using Q-Q plots of residuals. Data with skewed distributions will be log-transformed or non-linear mixed effects models will be used. All participants will be included in the intention-to-treat (ITT) analyses and missing data will not be imputed, per contemporary guidelines with use of linear mixed models [10].

Sample Size

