We will recruit 12 participants to be included in this cross-over study, which has blood β-OHB (as represented by the area under the curve across the 4 hours following ingestion of the supplement) as the primary outcome. A previous pharmacokinetic study exploring the effects of a ketone monoester provided at a dose of \sim 10 g in healthy adults found that blood β -OHB was raised to 1.4 \pm 0.6 mM within 30 minutes, and to an average of 0.5 ± 0.5 mM across the entire 4-hour post-supplementation period [2], which represents an effect size of d > 1.0compared to baseline. Using the outcome data from this study (N = 15) and assuming 80% power with an alpha level of 0.05 and a moderate correlation between repeated measures of 0.5, a total sample size of N = 6 would be sufficient to detect an increase in average blood β-OHB compared to baseline (calculated using G*Power v3.1). In order to allow for a more nuanced evaluation of differences between ketone supplements and to account for any dropouts or missing blood samples, we will recruit 12 participants (aiming for equal males and females), which is in line with the sample size of previous pharmacokinetic studies of ketone supplements [2].

Significance

The results of this study will help determine the effect of different types of ketone supplements on blood β -OHB and glucose. This is a pilot study and it will provide useful data to better answer future research questions and aid in the design of longer-term studies.

Outcome Measurements and Methods

The primary outcome will be total β -OHB as represented by the area under the curve across 4 hours. Secondary outcomes include blood glucose, blood pressure, heart rate, hunger and fullness, gastrointestinal discomfort, and taste and supplement acceptability.

Anthropometric Measures

Waist circumference (cm), height (cm), and weight (kg) will be measured using standard procedures. Body mass index (BMI) will be calculated as kg/m².

Physiological Measures

Resting blood pressure and heart rate will be collected for descriptive purpose and throughout the study visits (at the same time points as blood samples are collected). Before measurements, participants will be instructed to sit quietly and rest for 5 minutes. A finger tip heart rate monitor will track heart rate. Blood pressure will be collected using a cuff around the upper arm, a stethoscope will be placed in the cubital fossa for systolic and diastolic blood pressure.

Blood Sampling

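### The primary outcome is the 4-hour β-OHB AUC, but the only model written analyses time-point readings and tests no AUC difference, logged or not

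*Combined protocol and SAP*

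**What the plan says.** All references are to the combined protocol and SAP.

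- **Outcome.** Experimental design, and again Outcome Measurements and Methods: "The primary outcome will be total β -OHB as represented by the area under the curve across 4 hours".
- **Sampling.** β-OHB is read "at baseline and 15, 30, 60, 90, 120, 180, and 240 minutes after ingestion of the ketone supplement", which is eight readings at unequal intervals.
- **Model.** Statistical Analyses specifies, for data across time, "a linear mixed effects model with subjects as a random factor and condition and time as fixed factors". There is no supplement-by-time term, no visit-level term, no AUC derivation and no weighting of times.
- **Checks and fallback.** "Assumptions will be tested using Q-Q plots of residuals", followed by "Data with skewed distributions will be log-transformed or non-linear mixed effects models will be used". The fallback covers every outcome. It does not say whether readings or AUCs are logged, how to choose between its two options, or which curve the non-linear model would use.
- **Threshold.** "Significance will be set at P < 0.05".
- **Planning figures.** Under Sample Size, about 10 g of monoester raised β-OHB to 1.4 ± 0.6 mM within 30 minutes and "to an average of 0.5 ± 0.5 mM across the entire 4-hour post-supplementation period".

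**The concern.** An AUC weights each reading by the time it stands for. A model with supplement and time effects on balanced data weights each reading equally. The two agree when all supplements have curves of the same shape and can disagree when the shapes differ. The Background says that little is known about the kinetics of the two new products and that they can be expected to differ from the original ones, so different shapes are the expected case here.

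At stake is the main comparison. A product could be reported as giving more or less total β-OHB than the monoester when the areas are equal, or a real difference in area could be misstated. The fallback does not correct this. It changes the scale of the readings, or swaps in an unspecified model after the data have been seen, and neither step brings in the AUC.

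**Working it through.** **1. The plan's own figures.** A 4-hour average of 0.5 mM is an AUC of 0.5 × 240 = 120 mM·min (2.0 mM·h). The stated N = 6 for a rise from baseline can be reproduced with a repeated-measures ANOVA, taking f = d/2 = 0.5, ρ = 0.5 and λ = N·m·f²/(1 − ρ). With m = 6 measurements, λ = 6 × 6 × 0.25/0.5 = 18 and power is 0.85. With m = 7, λ = 21 and power is 0.89. The plan does not state m. This is background, since the point does not turn on N.

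**2. Weights.** The trapezoid weight of a reading is half the sum of its adjacent intervals, divided by 240.

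| Minute | 0 | 15 | 30 | 60 | 90 | 120 | 180 | 240 |
|---|---|---|---|---|---|---|---|---|
| AUC | 0.031 | 0.063 | 0.094 | 0.125 | 0.125 | 0.188 | 0.250 | 0.125 |
| Model | 0.125 | 0.125 | 0.125 | 0.125 | 0.125 | 0.125 | 0.125 | 0.125 |

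The first three readings carry 3/8 = 0.375 of the model's weight, against 0.1875 in the AUC. The 180-minute reading carries half the weight it has in the AUC.

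**3. Curves with equal AUC (assumed).** A is built to match the plan's 1.4 mM at 30 minutes and 0.5 mM average. B and C are flatter and scaled to the same area. The baseline of 0.10 mM is assumed.

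- A: 0.10, 0.90, 1.40, 0.95, 0.60, 0.35, 0.15, 0.10. Area 7.5 + 17.25 + 35.25 + 23.25 + 14.25 + 15 + 7.5 = 120.
- B: 0.100, 0.251, 0.402, 0.554, 0.654, 0.654, 0.503, 0.352. Area 120.
- C: 0.100, 0.523, 0.840, 0.893, 0.735, 0.523, 0.259, 0.153. Area 120.

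The model's raw contrast compares plain means: A 4.55/8 = 0.569, B 3.47/8 = 0.434, C 4.026/8 = 0.503. A reads 0.569/0.434 = 1.31 times B although the areas are equal. The logged contrast compares geometric means: A 0.373, B 0.379, C 0.395. These also differ, by up to 0.395/0.373 = 1.06.

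**4. How often P < 0.05 at equal AUC.** N = 12, 10,000 runs, log-normal variation with between-participant SD 0.30, reading SD 0.35 and visit SD 0 unless stated. Mixes are linear blends of A and B. The model columns use the stated additive model.

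| Comparison | Model, raw | Model, logged | AUC per visit | log(AUC) per visit |
|---|---|---|---|---|
| A v A (same shape) | 2.6% | 4.8% | 4.6% | 5.0% |
| A v 75% A + 25% B | 8.2% | 32.2% | 4.5% | 4.7% |
| A v 50% A + 50% B | 31.8% | 40.4% | 4.4% | 4.7% |
| A v 25% A + 75% B | 65.5% | 15.6% | 4.4% | 4.9% |
| A v B | 88.0% | 0.1% | 4.9% | 4.9% |
| A v C | 28.0% | 13.2% | 4.9% | 5.4% |
| A, B, C | 81.9% | 1.2% | 4.4% | 4.8% |
| A, B, C, visit SD 0.15 | 74.5% | 9.7% | 4.9% | 5.2% |

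The very low logged figures are no safeguard. Without a supplement-by-time term, differences in shape go into the residual and inflate it. Adding that term does not repair the test: in the different-shape pairs, rejection was then 10-98% raw and 6-58% logged.

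**5. A second set of curves.** The peaked curve 0.1, 0.8, 1.4, 1.0, 0.6, 0.4, 0.2, 0.1 has area 6.75 + 16.5 + 36 + 24 + 15 + 18 + 9 = 125.25 mM·min. Against three assumed flatter curves of the same area, the stated additive model rejected in about 34-64% of trials raw and 10-39% logged. Per-visit AUC or log(AUC) rejected in about 4-6%. Part of the model's excess comes from having no visit-level term: the eight readings of one visit share variation that the model treats as independent. The rows in step 4 with visit SD 0 exclude that contribution and still show the problem.

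**The case against.** **The rule can be read charitably.** It speaks of data, not of readings, and it also covers glucose, blood pressure and ratings, which have no stated AUC target. If the AUC is what gets logged, the rule is sound. This stands, so the rule is best called ambiguous for the primary outcome. It does not rescue the plan, because no AUC analysis is written to which the rule could apply.

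**A reader might infer that logging is what breaks the link to AUC.** The documents do not support that. The unlogged model has no such link either. Logging lowered the error in three of the five different-shape pairs in the table and in both three-curve rows.

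**A reader might also infer a larger error.** A time-weighted mean of logs rejects in 43-73% of trials under another assumed pair of equal-AUC curves. The plan states no such weights, and the same pair unweighted gives 7-8%.

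**Nor is it shown that the fallback will be needed.** A normal distribution with mean 0.5 and SD 0.5 puts Φ(−1) = 16% below zero, which suggests skew. But that figure describes a 4-hour average, the 30-minute figure gives Φ(−1.4/0.6) = 1%, and the planned check looks at residuals.

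**The non-linear option is not wrong in principle.** A specified curve model could yield AUC as a derived quantity. What stands is that none is specified, and that a non-linear mean does not in itself cure skewed residuals.

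**The study is an exploratory pilot** with no hypotheses on how the supplements differ. That limits the consequence. It still names a primary outcome, sets a significance level and aims to compare the products.

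**Conclusion.** Wrong as written: the stated model does not test the stated primary outcome, on the raw or the log scale. That follows from the weights alone and needs no simulation. Its size does depend on assumptions about curve shapes, baseline and variance components, none of which the plan gives. Under those tried in the second set, false differences at equal AUC run at about 34-64% raw and 10-39% logged, partly from the missing visit term, against about 4-6% for per-visit AUC or log(AUC). Other assumed shapes give values outside these ranges in both directions. If all supplements had the same curve shape, the weighting problem would vanish. The consequence is moderate, given the pilot status. An argument that zero readings cannot be logged is left out, because it rests on a meter resolution that the documents do not give.

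**What to change.** Add to Statistical Analyses: *For the primary outcome, the 4-hour AUC of β-OHB is computed for each participant and visit by the trapezoid rule on the original scale. Log(AUC) is compared between supplements in a mixed model with participant as random effect and reported as ratios of geometric means. Untransformed AUC is analysed as a sensitivity analysis. The model for readings across time is used only to describe curve shape. A non-linear mixed model is not used as the remedy for skewness in the primary outcome.*

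The cost is a few sentences, with no change to visits, sampling or sample size. The main downside is that the primary result becomes a ratio instead of a difference in mM·h; the sensitivity analysis supplies the difference. A per-visit AUC also needs a line on how a missed finger prick is handled, since the plan currently leaves missing readings to the time-point model.
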